6.0 Other Relevant Data Analyses and Summaries

6.1 Subject Completion

A table will be constructed with counts of screen failures and enrolled subjects. Of those enrolled, counts and percentages of the number of subjects withdrawing from the study before study completion and the number completing the study will be displayed. For those subjects that withdraw before completion of the study, counts and percentages of the reasons for withdrawal will be tabulated. The table will include summary counts and percentages by dose group and overall. A data listing of all subject completion and withdrawal data will also be constructed.

6.2 Study Drug Administration

The mass dose and radioactivity of Tc 99m tilmanocept injected will be summarized by dose group and overall.

6.3 Subject Imaging

Each subject will undergo whole body planar imaging. SPECT/CT imaging of region(s) of interest is optional for each subject. Results of all imaging procedures will be listed.

7.0 List of Analysis Tables, Figures and Listings

Table No.	Table Title	Included in Final Tables	Shown in Appendix B
1	Subject Disposition by Cohort	X	X
2	Demographics and Baseline Data Summary Statistics by Cohort – Continuous Variables (Safety Population)	X	X
3	Demographics and Baseline Data Summary Statistics by Cohort – Categorical Variables (Safety Population)	X	X
4	Summary of Study Drug Administration by Cohort (Safety Population)	X	X
5	Subject-Level Localization of KS Lesions – Nuclear Medicine Findings (ITD Population)	X	X
6	Lesion-Level Localization of KS Lesions – Nuclear Medicine Findings (ITD Population)	X	X
7	Additional KS Lesions Identified from Imaging That Were Not Seen Clinically – Nuclear Medicine Findings (ITD Population)	X	X
8	Lesion-Level Non-Localization of KS Lesions – Nuclear Medicine Findings (ITD Population)	X	X
9	Number and Percentage of Concordant and Reverse Concordant Lesions (ITD Population)	X	X
10	Summary of Imaging-Localized Biopsied Lesion Localization Intensity by Cohort – Imaging = Planar (ITD Population)	X	X
11	Summary of Imaging-Localized Biopsied Lesion Localization Intensity by Cohort – Imaging = SPECT/CT (ITD Population)	X	X
12	Summary of Per Biopsied Lesion Proportion of CD206-Expressing Cells and Proportion of HHV8-Expressing Cells by IHC (ITD Population)	X	X
13	Summary of Per Biopsied Lesion HHV8 Quantitation by qPCR (ITD Population)	X	X
14	Subject-Level Localization in Areas Other Than KS Sites – Nuclear Medicine Findings (ITD Population)	X	X
15	Site-Level Localization in Areas Other Than KS Sites – Nuclear Medicine Findings (ITD Population)	X	X
16	Number and Percent of Subjects with Adverse Events (Safety Population)	X	X
17	Summary of Adverse Events (Safety Population)	X	X
18	Number and Percent of Subjects with Treatment Emergent Adverse Events (Safety Population)	X	X
19	Summary of Treatment Emergent Adverse Events (Safety Population)	X	X
20	Number and Percent of Subjects with Adverse Drug Reactions (Safety Population)	X	X
21	Number and Percent of Subjects with Serious Adverse Events (Safety Population)	X	X
22	Vital Sign Parameters Summary Statistics (Safety Population)	X	X

Table No.	Table Title	Included in Final Tables	Shown in Appendix B
23	Vital Sign Shift Table (Safety Population)	X	X
24	Clinical Laboratory Parameters Summary Statistics (Safety Population)	X	X
25	Clinical Laboratory Parameters Shift Table (Safety Population)	X	X
26	Electrocardiogram Parameters Summary Statistics (Safety Population)	X	X
27	Electrocardiogram Shift Table (Safety Population)	X	X
28	Number and Percent of Subjects Taking Concomitant Medications (Safety Population)	X	X

Listing No.	Data Listing Title	Included in Final Listings	Shown in Appendix B
DL1	Subject Disposition Data Listing	X	X
DL2	Inclusion/Exclusion Data Listing	X	X
DL3	Protocol Deviations Data Listing	X	X
DL4	Demographics Data Listing	X	X
DL5	Subjects Excluded from ITD Population Data Listing	X	X
DL6	Medical History Data Listing	X	X
DL7	Prior and Concomitant Medications Data Listing	X	X
DL8	Adverse Events Data Listing	X	X
DL9	Subject Laboratory Profiles - Hematology Data Listing	X	X
DL10	Subject Laboratory Profiles – Serum Chemistry Data Listing	X	X
DL11	Subject Laboratory Profiles – Urinalysis Data Listing	X	X
DL12	Electrocardiogram Data Listing	X	X
DL13	Physical Exam Data Listing	X	X
DL14	Vital Signs Data Listing	X	X
DL15	Study Drug Administration Data Listing	X	X
DL16	Post-Injection Imaging Data Listing	X	X
DL17	Quantitative Imaging Results Data Listing	X	X
DL18	Qualitative Imaging Results Data Listing	X	X
DL19	Lesion Biopsy Results Data Listing	X	X
DL20	Clinical KS Lesion Assessment Listing	X	X
DL21	Telephone Follow Up Contact Data Listing	X	X

Appendix A – Tables, Figures and Listing Specifications

Orientation

Tables, figures, and listings will be displayed in landscape.

Margins

Margins will be 1 inch on all sides. Table, figure, and listing boundaries will not extend into the margins.

Font

Courier New, 8 point.

Headers

The table number will be on the second line of the title area. The title area will contain the Sponsor name, the study number, and the name of the table. The title area will contain the page number (Page x of y) on the far right, one line above the name of the table.

Footers

- The first line will be a solid line.
- Next will be any footnotes regarding information displayed in the table.
- Below these footnotes will be displayed “STATKING Clinical Services (Date)” on the far left.
- The last line will display the name of the SAS program that generated the table and (if applicable) the source data reference.

Table Disclaimer

The format of the mock tables shown in the appendix of this Statistical Analysis Plan (SAP) will be the format of the deliverable tables to the extent that Word document constructed tables can match production tables produced by SAS. This formatting includes the content and format of the header and footer areas of the tables. The Sponsor agrees to the format of the tables as shown in the appendix.

Further programming charges will be applicable for changes in the format of tables (including title statements, notes, data dependent footnotes, etc.) made after the approval of the SAP.

Missing Values

All missing values will be displayed on the output tables/listings as blanks.

Computation Values for Study Dates

The date format to be used is dd-mmm-yyyy. Missing parts of dates are not shown (e.g., for a missing day value, the value displayed is in mmm-yyyy format). When date computations are necessary, the following table indicates the substitutions used in order to make those computations.

Scenario	Value Used for Computations
Start date – Missing month and day values	January 1 of the indicated year
Start date – Missing day values	The first day of the indicated month
Stop date – Missing month and day values	December 31 of the indicated year
Stop date – Missing day values	The last day of the indicated month

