8.6 Safety

8.6.1 Adverse Events

8.6.1.1 Definition of Adverse Event

The definitions below follow International Conference on Harmonization (ICH) – Good Clinical Practice (GCP) (see also ICH Guideline for Clinical Safety Data Management: Definitions and Standards for Expedited Reporting).

Adverse Event (AE)

An AE is defined as any untoward medical occurrence in a subject administered a pharmaceutical product and which does not necessarily have a causal relationship with this treatment. An AE can therefore be any unfavorable and unintended sign (including an abnormal laboratory finding), symptom, or disease temporally associated with the use of a medicinal (investigational) product, whether or not considered related to the medicinal (investigational) product.

Any clinically significant change in a condition (worsening) from screening that results in a change in subject management will be considered an AE and will be recorded on the AE page of the CRF.

By definition for this study, all untoward medical occurrences beginning on the day of Visit 2 Baseline (Day 1) through the Follow-up Phone Call are to be reported as AEs. AEs continuing after study completion will be followed to normalization or stabilization. Additionally, untoward medical events occurring prior to the day of Tc 99m tilmanocept administration will be collected and added to the subject's medical history unless they are related to a study procedure, in which case the event will be recorded as an AE. SAEs will be reported from the time of consent through the end of participation.

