8.6.1.3 Assessments and Documentation of Adverse Events

Attention shall be paid to the occurrence of AEs for the duration of subject participation. Events occurring prior to Visit 2 (day of Tc 99m tilmanocept administration) will be recorded in the subject's medical history unless determined to be related to the study procedure. Untoward medical events beginning on Visit 2 (day of Tc 99m tilmanocept administration) through the completion of the Follow-up Phone Call will be reported as adverse events. Thus, subjects should be closely observed by the investigator both during and after the evaluation.

Any AE (observed, volunteered, or elicited) should be recorded in detail in the source documentation.

The following information is required:

- The **date and time of onset** of any AE.
- The duration (the entire duration of an event or symptom, calculated from date of onset to date of end, if not recorded directly).
- The seriousness of the AE will be assessed by the investigator. If the investigator deems that an AE qualifies as an SAE, a special form provided by the sponsor should be completed and the event must be immediately reported to the sponsor. A definition of SAEs is provided in [Section 8.6.1.5](#).
- The maximum intensity (mild, moderate, or severe).
- Whether drug treatment was administered for the event, any specific drug treatment must be documented.
- The relationship of the AE to the investigational product and to study conduct (for definitions, see above).

The **outcome** of the AE (resolved, resolved with sequelae, not resolved, unknown, death).

AEs will be coded according to an internationally recognized dictionary (Medical Dictionary for Regulatory Activities [MedDRA]).

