9.5.4 Analysis of Safety Variables

The number and percentage of subjects with ADRs will be tabulated by dose group and overall.

All AEs will be observed for each subject from the time of signing of informed consent until exit from the study. A treatment emergent adverse event (TEAE) is defined as an adverse event whose start date is on or after the Tc 99m tilmanocept injection date and time. If the injection date and time and/or the AE start date are missing, the AE will be considered treatment emergent.

Prior to analysis, all AEs will be coded using the MedDRA coding dictionary. Based on these coded terms, treatment emergent AEs will be summarized by dose group and overall as follows:

- by system organ class and preferred terms
- by system organ class and preferred terms and relation to study drug
- by system organ class and preferred terms and severity

Observed and change from baseline vital sign parameters, ECG parameters and hematology, clinical chemistry and urinalysis parameters will be summarized using descriptive statistics (mean, median, standard deviation, minimum, maximum and range) by dose group and overall.

Other safety analyses will be described in the SAP for the study.

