5.0 Analysis of Safety

Adverse Drug Reactions (ADRs) are defined as all noxious and unintended responses to a medicinal product related to any dose or dose regimen. The phrase 'responses to a medicinal product' means that a causal relationship between a medicinal product and an adverse event. The primary safety variable is the proportion of patients experiencing at least one ADR. The number and percentage of subjects with ADRs will be tabulated by dose group and overall. Other safety endpoints are noted below.

Analysis of Safety Endpoints

Attention shall be paid to the occurrence of adverse events (AEs) from the time of signing informed consent until exit from the study. Events occurring prior to Tc 99m tilmanocept administration will be recorded in the subject's medical history unless determined to be related to the study procedure. A treatment emergent adverse event (TEAE) is defined as an adverse event whose start date is on or after the first study drug administration date. If the study drug administration date and/or the AE start date are missing, the AE will be considered treatment emergent.

Prior to analysis, all AEs will be coded using the Medical Dictionary for Regulatory Activities (MedDRA). The MedDRA version used will be stated in the final validated tables. Based on these coded terms, AEs and TEAEs will be summarized by dose group and overall as follows:

- by system organ class and preferred terms;
- by system organ class and preferred terms and relation to study drug; and,
- by system organ class and preferred terms and severity.

In addition to the above endpoints, the following describes the analyses of the other safety data being collected for the study.

Vital Signs

Vital signs will include heart rate, blood pressure, respiration rate, and body temperature. Vital signs will be taken during screening, prior to study drug administration on Day 1 (and Day 7 [\pm 3] for Cohort 3), and within 30 minutes following study drug administration. For each vital sign, summary statistics

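### Read literally, the SAP's partial-date rule drops most post-injection adverse events with an incomplete onset date from the TEAE tables, while events with no onset date are kept

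*SAP*

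**What the plan says.** SAP 5.0 defines a treatment-emergent event as an "adverse event whose start date is on or after the first study drug administration date". This is a comparison of two dates. For absent dates it adds: "If the study drug administration date and/or the AE start date are missing, the AE will be considered treatment emergent". Protocol 9.5.4 has the same default: "If the injection date and time and/or the AE start date are missing, the AE will be considered treatment emergent". Neither text says how a date with only some parts known is to be classified.

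SAP Appendix A, under its rules for study dates, covers partial dates in general: "When date computations are necessary, the following table indicates the substitutions used in order to make those computations". A start date lacking the day becomes "The first day of the indicated month". One lacking month and day becomes "January 1 of the indicated year". The rows are not limited to medical history or medications, and adverse event onset is not excepted.

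On which records enter the adverse event dataset, Protocol 8.6.1.3 reports as adverse events "Untoward medical events beginning on Visit 2 (day of Tc 99m tilmanocept administration) through the completion of the Follow-up Phone Call". Earlier events go to medical history unless they are related to a study procedure, and SAP 5.0 repeats this. Protocol 8.6.1.1 adds that serious events are reported from consent.

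**The concern.** Taken together, the rules order the cases the wrong way round. An event with no onset date is counted as treatment-emergent. An event known to have begun in the month of injection is moved to the 1st of that month. It then precedes the injection and fails the TEAE test unless the subject was injected on the 1st. Better information gives the less conservative classification.

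The collection rule makes this harder to justify. Almost every adverse event record began on or after Day 1, so a partial date in that dataset nearly always belongs to a post-injection event. The substitution therefore errs in the anti-conservative direction.

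What is at stake is the completeness of Tables 18 and 19 and of the treatment-emergent column in Listing 8. Listing 8 also shows the most recent tilmanocept injection for each event. In Cohort 3, when both injections fall in the stated month, an onset set to the 1st normally precedes both, so that column could not be filled correctly.

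**Working it through.** The plan gives no figure on this point, so there is none to reproduce. The check applies the two SAP rules to events that truly began on or after the first injection and counts those that fail the TEAE test.

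**Inputs**
- Substitution values: SAP Appendix A, as above.
- TEAE test: start date not earlier than the first injection date (SAP 5.0).
- Follow-up in Cohorts 1 and 2: call 4 to 10 days after injection (Protocol 7.3).
- Follow-up in Cohort 3: IV injection on Day 4 to 10, which is 3 to 9 days after the Day 1 SC injection (Protocol 7.5), then a call 4 to 10 days later (Protocol 7.6). The maximum is 9 + 10 = 19 days after the first injection.
- Calendar: recruitment January 2018 to June 2019 (Protocol Synopsis), i.e. 365 + 181 = 546 days in 18 months.
- Assumptions: injections spread evenly over those 546 days; onset uniform over 0 to W days after the first injection.

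**One case.** Injection on 12 March, onset recorded as March. The onset becomes 1 March, 11 days before injection, and the event is not a TEAE.

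**Day missing.** A month of L days has L(W+1) combinations of injection day and onset delay. An event stays treatment-emergent in two situations:
- the injection is on the 1st: W+1 combinations;
- the onset falls in the next month: 1 + 2 + … + W = W(W+1)/2 combinations.

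Dividing by W+1 and summing over 18 months gives: share lost = 1 − 18(1 + W/2)/546.

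**Month and day missing.** Events survive only if the injection is on 1 January (two such days in the period) or the onset crosses the single year-end within it: share lost = 1 − (2 + W/2)/546.

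| W (days) | Day missing | Month and day missing |
|---|---|---|
| 0 | 1 − 18/546 = 96.7% | 1 − 2/546 = 99.6% |
| 4 | 1 − 54/546 = 90.1% | 1 − 4/546 = 99.3% |
| 7 | 1 − 81/546 = 85.2% | 1 − 5.5/546 = 99.0% |
| 10 | 1 − 108/546 = 80.2% | 1 − 7/546 = 98.7% |
| 13 | 1 − 135/546 = 75.3% | 1 − 8.5/546 = 98.4% |
| 19 | 1 − 189/546 = 65.4% | 1 − 11.5/546 = 97.9% |

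Direct enumeration of every injection date and delay gives the same values. Restricting injections to weekdays changes them by less than 0.3 points.

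**Dependence on the injection date.** With the day missing, an injection on the 1st loses nothing. For an injection on 28 June with onset 0–7 days later, 28, 29 and 30 June are moved to 1 June and lost, while 1 to 5 July are moved to 1 July and kept: 3/8 = 38% lost.

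**Effect on a table.** Table 18 percentages count subjects. If the lost event is that subject's only TEAE, the cohort percentage falls by 1/4 = 25 points with four subjects or 1/6 = 17 points with six. If the subject has another TEAE, the subject-level percentage does not change.

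**Wholly missing onset date.** None are lost, because the SAP 5.0 default applies.

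**The case against.** The strongest reply is that SAP 5.0 is the specific safety rule and Appendix A a general output specification that applies only when a computation is needed. If a partial date counts as missing under SAP 5.0, no computation arises and nothing is lost. That reading is possible. But Appendix A treats partial dates as a case of its own with its own values, and nothing says that SAP 5.0 takes precedence. The literal reading drops the events, and the ambiguity alone would call for a clarifying sentence.

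The second reply is that no event leaves the safety report. This stands. Tables 16 and 17 present all adverse events in the same layout as Tables 18 and 19, so a dropped event would show as a difference between them. Appendix A also prints partial dates without the imputed part, so Listing 8 would reveal the case.

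The third reply is that partial dates will be rare. This also stands: Protocol 8.6.1.3 requires the date and time of onset, follow-up is short, and monitors compare the eCRFs with source. A year-only onset is especially unlikely, so the 98–99% figure describes an improbable case.

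Three stronger readings are tempting and are not supported:
- Because safety is the primary objective, a reader might infer that the primary result is biased. The primary endpoint is the proportion of subjects with an ADR. Table 20 defines ADRs by causality with no treatment-emergent condition, and escalation in Protocol 5.3 also rests on ADRs.
- A reader might infer that the SAP contradicts the protocol. Protocol 8.6.1.1 defines adverse events, not treatment-emergent ones, and the affected events remain adverse events. Protocol 9.5.4 is as silent on partial dates as SAP 5.0.
- A reader might infer that every partly dated event is lost. Injections on the 1st and onsets in a later month than the injection are exceptions.

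**Conclusion.** The concern holds as a defect in the stated rules, limited to secondary safety displays. Followed literally, SAP 5.0 and Appendix A would class most partly dated post-injection events as pre-treatment while keeping wholly undated ones. The averaged loss is about 80% (onset 0–10 days) to 65% (0–19 days) with the day missing, and about 98–99% with month and day missing. These shares rest on evenly spread injections and uniform onset, and on partial dates not being covered by the missing-date default. They are shares of events with a partial onset date, not of all events, and few such events are expected. The affected outputs are Tables 18 and 19 and the treatment-emergent flag in Listing 8. The ADR endpoint (Table 20), dose escalation, the all-AE tables (16, 17) and the SAE table (21) do not use the flag. The most that one lost event can do is move a cohort's TEAE percentage by 17 to 25 points, and only if that subject has no other TEAE. The repair is cheap enough to justify making the change.

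**What to change.** Exempt adverse event onset from the Appendix A start-date rows for TEAE classification, leaving those rows in place for medical history and medications. Add to SAP 5.0:

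*An AE with a partial start date is treatment-emergent unless the known part of the start date, or the stop date, shows that it began before the first injection. If a date is needed for computation, use the later of the first injection date and the earliest date compatible with the known part.*

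The second sentence covers both situations: injection on 12 March with onset in March gives 12 March, and injection on 28 June with onset in July gives 1 July. Under this rule no truly post-injection event is misclassified in any scenario above.

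In Listing 8, for Cohort 3, show the most recent injection as undetermined when the known part of the date is compatible with onset after either injection. Otherwise, using the first injection date would assign every such event to the SC injection.

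The cost is two sentences in the SAP, a listing convention and a small programming change. The downside is that an occasional pre-injection event held in the adverse event dataset, such as a procedure-related one, may be counted as a TEAE. That matches the SAP's own handling of events with no date.

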Appendix B – Table Shells

Table 1. Subject Disposition by Cohort
Navidea Biopharmaceuticals - Study No. NAV3-24

		Cohort 1	Cohort 2	Cohort 3	Overall
Screen Failures		xx	xx	xx	xx
Enrolled		xx	xx	xx	xx
Completed		xx (xxx%)	xx (xxx%)	xx (xxx%)	xx (xxx%)
Withdrawn		xx (xxx%)	xx (xxx%)	xx (xxx%)	xx (xxx%)
Reason for Withdrawal	Adverse Event	xx (xxx%)	xx (xxx%)	xx (xxx%)	xx (xxx%)
	Lost To Follow-Up	xx (xxx%)	xx (xxx%)	xx (xxx%)	xx (xxx%)
	Death	xx (xxx%)	xx (xxx%)	xx (xxx%)	xx (xxx%)
	Physician Decision	xx (xxx%)	xx (xxx%)	xx (xxx%)	xx (xxx%)
	Protocol Deviation	xx (xxx%)	xx (xxx%)	xx (xxx%)	xx (xxx%)
	Study Terminated by Sponsor	xx (xxx%)	xx (xxx%)	xx (xxx%)	xx (xxx%)
	Withdrawal by Subject	xx (xxx%)	xx (xxx%)	xx (xxx%)	xx (xxx%)
	Other	xx (xxx%)	xx (xxx%)	xx (xxx%)	xx (xxx%)

The denominator for all percentages in the table is the number of enrolled subjects in the respective cohort and overall.

Cohort 1 = 100µg/5mCi IV; Cohort 2 = 100µg/10mCi IV; Cohort 3 = 200µg/5mCi IV and SC.

STATKING Clinical Services (DD-MMM-YYYY)

Source Program: xxxxxxx.sas

Page x of y

Table 2. Demographics and Baseline Data Summary Statistics by Cohort - Continuous Variables
 Navidea Biopharmaceuticals - Study No. NAV3-24
 Safety Population (N=xxx)

Variable	Group	Mean	Std Dev	n	Min	Max	Median
Age (years)	Cohort 1	xxx	xxx	xxx	xxx	xxx	xxx
	Cohort 2	xxx	xxx	xxx	xxx	xxx	xxx
	Cohort 3	xxx	xxx	xxx	xxx	xxx	xxx
	Overall	xxx	xxx	xxx	xxx	xxx	xxx
Height (in)	Cohort 1	xxx	xxx	xxx	xxx	xxx	xxx
	Cohort 2	xxx	xxx	xxx	xxx	xxx	xxx
	Cohort 3	xxx	xxx	xxx	xxx	xxx	xxx
	Overall	xxx	xxx	xxx	xxx	xxx	xxx
Weight (lb)	Cohort 1	xxx	xxx	xxx	xxx	xxx	xxx
	Cohort 2	xxx	xxx	xxx	xxx	xxx	xxx
	Cohort 3	xxx	xxx	xxx	xxx	xxx	xxx
	Overall	xxx	xxx	xxx	xxx	xxx	xxx
Number of KS lesions ^a	Cohort 1	xxx	xxx	xxx	xxx	xxx	xxx
	Cohort 2	xxx	xxx	xxx	xxx	xxx	xxx
	Cohort 3	xxx	xxx	xxx	xxx	xxx	xxx
	Overall	xxx	xxx	xxx	xxx	xxx	xxx

^a Number of KS lesions identified in screening, including cutaneous and non-cutaneous lesions.

Cohort 1 = 100µg/5mCi IV; Cohort 2 = 100µg/10mCi IV; Cohort 3 = 200µg/5mCi IV and SC.

STATKING Clinical Services (DD-MMM-YYYY)

Source Program: xxxxxxxx.sas

Table 3. Demographics and Baseline Data Summary Statistics by Cohort - Categorical Variables
 Navidea Biopharmaceuticals - Study No. NAV3-24
 Safety Population (N=xxx)

Demographics Variable	Category	Cohort 1 (N=xxx)	Cohort 2 (N=xxx)	Cohort 3 (N=xxx)	Overall (N=xxx)
Gender	Male	xxx (xxx%)	xxx (xxx%)	xxx (xxx%)	xxx (xxx%)
	Female	xxx (xxx%)	xxx (xxx%)	xxx (xxx%)	xxx (xxx%)
Race	American Indian or Alaska Native	xxx (xxx%)	xxx (xxx%)	xxx (xxx%)	xxx (xxx%)
	Asian	xxx (xxx%)	xxx (xxx%)	xxx (xxx%)	xxx (xxx%)
Race	Black or African American	xxx (xxx%)	xxx (xxx%)	xxx (xxx%)	xxx (xxx%)
	Native Hawaiian or Other Pacific Islander	xxx (xxx%)	xxx (xxx%)	xxx (xxx%)	xxx (xxx%)
Race	White	xxx (xxx%)	xxx (xxx%)	xxx (xxx%)	xxx (xxx%)
	Other	xxx (xxx%)	xxx (xxx%)	xxx (xxx%)	xxx (xxx%)
Ethnicity	Hispanic or Latino	xxx (xxx%)	xxx (xxx%)	xxx (xxx%)	xxx (xxx%)
	Not Hispanic or Latino	xxx (xxx%)	xxx (xxx%)	xxx (xxx%)	xxx (xxx%)

Cohort 1 = 100µg/5mCi IV; Cohort 2 = 100µg/10mCi IV; Cohort 3 = 200µg/5mCi IV and SC.
 STAKING Clinical Services (DD-MMM-YYYY)
 Source Program: xxxxxxxx.sas

Page x of y

Table 4. Summary of Study Drug Administration by Cohort
 Navidea Biopharmaceuticals - Study No. NAV3-24
 Safety Population (N=xxx)

	Group	Mean	Std Dev	n	Min	Max	Median
Tc 99m Dose (mCi)	Cohort 1 IV	xxxx	xxxx	xx	xxxx	xxxx	xxxx
	Cohort 2 IV	xxxx	xxxx	xx	xxxx	xxxx	xxxx
	Cohort 3 IV	xxxx	xxxx	xx	xxxx	xxxx	xxxx
	Cohort 3 SC	xxxx	xxxx	xx	xxxx	xxxx	xxxx
Mass Dose (µg)	Cohort 1 IV	xxxx	xxxx	xx	xxxx	xxxx	xxxx
	Cohort 2 IV	xxxx	xxxx	xx	xxxx	xxxx	xxxx
	Cohort 3 IV	xxxx	xxxx	xx	xxxx	xxxx	xxxx
	Cohort 3 SC	xxxx	xxxx	xx	xxxx	xxxx	xxxx

Cohort 1 = 100µg/5mCi IV; Cohort 2 = 100µg/10mCi IV; Cohort 3 = 200µg/5mCi IV and SC.

STATKING Clinical Services (DD-MMM-YYYY)

Source Program: xxxxxxxx.sas

Table 5. Subject-Level Localization of KS Lesions-Nuclear Medicine Findings
 Navidea Biopharmaceuticals - Study No. NAV3-24
 ITD Population (N=xxx)

Group	Number of Subjects	Number (Proportion) Localized	95% Exact One-Sided Binomial CI for Proportion
Cohort 1 IV	xx	xxx (xxx)	(xxx, xxx)
Cohort 2 IV	xx	xxx (xxx)	(xxx, xxx)
Cohort 3 IV	xx	xxx (xxx)	(xxx, xxx)
Cohort 3 SC	xx	xxx (xxx)	(xxx, xxx)
All Cohorts Combined	xx	xxx (xxx)	(xxx, xxx)

Cohort 1 = 100 μ g/5mCi IV; Cohort 2 = 100 μ g/10mCi IV; Cohort 3 = 200 μ g/5mCi IV and SC.
 STATKING Clinical Services (DD-MMM-YYYY)
 Source Program: xxxxxxxx.sas

Table 6. Lesion-Level Localization of KS Lesions-Nuclear Medicine Findings
 Navidea Biopharmaceuticals - Study No. NAV3-24
 ITD Population (N=xxx)

Group	Number of Clinically Identified Lesions ^a	Number (Proportion) Localized by Imaging	95% Exact One-Sided Binomial CI for Proportion
Cohort 1 IV	xx	xxx (xxx)	(xxx, xxx)
Cohort 2 IV	xx	xxx (xxx)	(xxx, xxx)
Cohort 3 IV	xx	xxx (xxx)	(xxx, xxx)
Cohort 3 SC	xx	xxx (xxx)	(xxx, xxx)
All Cohorts Combined	xx	xxx (xxx)	(xxx, xxx)

^a Number of cutaneous and non-cutaneous lesions identified in screening.

Cohort 1 = 100 μ g/5mCi IV; Cohort 2 = 100 μ g/10mCi IV; Cohort 3 = 200 μ g/5mCi IV and SC.

STATKING Clinical Services (DD-MMM-YYYY)

Source Program: xxxxxxx.sas

Page x of y

Table 7. Additional KS Lesions Identified from Imaging That Were Not Seen Clinically - Nuclear
Medicine Findings
Navidea Biopharmaceuticals - Study No. NAV3-24
ITD Population (N=xxx)

Group	Number of Identified Lesions	Number (Proportion) of Subjects with at Least 1 Identified Lesion
Cohort 1 IV	xx	xxx (xxx)
Cohort 2 IV	xx	xxx (xxx)
Cohort 3 IV	xx	xxx (xxx)
Cohort 3 SC	xx	xxx (xxx)
All Cohorts Combined	xx	xxx (xxx)

Cohort 1 = 100 μ g/5mCi IV; Cohort 2 = 100 μ g/10mCi IV; Cohort 3 = 200 μ g/5mCi IV and SC.
STATKING Clinical Services (DD-MMM-YYYY)
Source Program: xxxxxxxx.sas

Table 8. Lesion-level Non-Localization of KS Lesions - Nuclear Medicine Findings
 Navidea Biopharmaceuticals - Study No. NAV3-24
 ITD Population (N=xxx)

Group	Number of Clinically Identified Lesions ^a	Number (Proportion) Not Localized by Imaging	95% Exact One-Sided Binomial CI for Proportion
Cohort 1 IV	xx	xxx (xxx)	(xxx, xxx)
Cohort 2 IV	xx	xxx (xxx)	(xxx, xxx)
Cohort 3 IV	xx	xxx (xxx)	(xxx, xxx)
Cohort 3 SC	xx	xxx (xxx)	(xxx, xxx)
All Cohorts Combined	xx	xxx (xxx)	(xxx, xxx)

^a Number of cutaneous and non-cutaneous lesions identified in screening.
 Cohort 1 = 100 μ g/5mCi IV; Cohort 2 = 100 μ g/10mCi IV; Cohort 3 = 200 μ g/5mCi IV and SC.
 STATKING Clinical Services (DD-MMM-YYYY)
 Source Program: xxxxxxxx.sas

Page x of y

Table 9. Number and Percentage of Concordant and Reverse Concordant Lesions
Navidea Biopharmaceuticals - Study No. NAV3-24
ITD Population (N=xxx)

IV Result	SC Result		Total	Concordance	Reverse Concordance	p-Value (McNemar's Test)
	Localized	Not Localized				
Localized	xx (xxx%)	xx (xxx%)	xx (xxx%)	xxx (xxx%)	xxx (xxx%)	xxx
Not Localized	xx (xxx%)	xx (xxx%)	xx (xxx%)			
Total	xx (xxx%)	xx (xxx%)				

STATKING Clinical Services (DD-MMM-YYYY)
Source Program: xxxxxxxx.sas

Page x of y

Table 10. Summary of Imaging-Localized Biopsied Lesion Localization Intensity by Cohort -
 Imaging = Planar
 Navidea Biopharmaceuticals - Study No. NAV3-24
 ITD Population (N=xxxx)

Group	Variable ^a	Mean	Std Dev	n	Min	Max	Median
Cohort 2 IV	Avg Pixel Intensity Percent Above Background	xx xx	xx xx	xx xx	xx xx	xx xx	xx xx
Cohort 3 IV	Avg Pixel Intensity Percent Above Background	xx xx	xx xx	xx xx	xx xx	xx xx	xx xx
All Cohorts Combined	Avg Pixel Intensity Percent Above Background	xx xx	xx xx	xx xx	xx xx	xx xx	xx xx

^a All summary statistics are performed on the subject level.

Cohort 1 = 100 μ g/5mCi IV; Cohort 2 = 100 μ g/10mCi IV; Cohort 3 = 200 μ g/5mCi IV and SC.

STATKING Clinical Services (DD-MMM-YYYY)

Source Program: xxxxxxxx.sas

Page x of y

Table 11. Summary of Imaging-Localized Biopsied Lesion Localization Intensity by Cohort -
 Imaging = SPECT/CT
 Navidea Biopharmaceuticals - Study No. NAV3-24
 ITD Population (N=xxxx)

Group	Variable ^a	Mean	Std Dev	n	Min	Max	Median
Cohort 2 IV	Avg Pixel Intensity Percent Above Background	xx xx	xx xx	xx xx	xx xx	xx xx	xx xx
Cohort 3 IV	Avg Pixel Intensity Percent Above Background	xx xx	xx xx	xx xx	xx xx	xx xx	xx xx
All Cohorts Combined	Avg Pixel Intensity Percent Above Background	xx xx	xx xx	xx xx	xx xx	xx xx	xx xx

^a All summary statistics are performed on the subject level.

Cohort 1 = 100 μ g/5mCi IV; Cohort 2 = 100 μ g/10mCi IV; Cohort 3 = 200 μ g/5mCi IV and SC.

STATKING Clinical Services (DD-MMM-YYYY)

Source Program: xxxxxxxx.sas

Table 12. Summary of Per Biopsied Lesion Proportion of CD206-Expressing Cells and Proportion of HHV8-Expressing Cells by IHC
Navidea Biopharmaceuticals - Study No. NAV3-24
ITD Population (N=xxxx)

Group	Variable	Mean	Std Dev	n	Min	Max	Median
Cohort 2	Proportion of CD206-Expressing Cells	xx	xx	xx	xx	xx	xx
	Proportion of HHV8-Expressing Cells	xx	xx	xx	xx	xx	xx
Cohort 3	Proportion of CD206-Expressing Cells	xx	xx	xx	xx	xx	xx
	Proportion of HHV8-Expressing Cells	xx	xx	xx	xx	xx	xx
All Cohorts Combined	Proportion of CD206-Expressing Cells	xx	xx	xx	xx	xx	xx
	Proportion of HHV8-Expressing Cells	xx	xx	xx	xx	xx	xx

Cohort 1 = 100 μ g/5mCi IV; Cohort 2 = 100 μ g/10mCi IV; Cohort 3 = 200 μ g/5mCi IV and SC.

STATKING Clinical Services (DD-MMM-YYYY)

Source Program: xxxxxxxx.sas

Page x of y

Table 13. Summary of Per Biopsied Lesion HHV8 Quantitation by qPCR
Navidea Biopharmaceuticals - Study No. NAV3-24
ITD Population (N=xxx)

Group	Variable (Unit)	Mean	Std Dev	n	Min	Max	Median
Cohort 2	HHV8 (RFU)	xx	xx	xx	xx	xx	xx
Cohort 3	HHV8 (RFU)	xx	xx	xx	xx	xx	xx

STATKING Clinical Services (DD-MMM-YYYY)
Source Program: xxxxxxxx.sas

Page x of y

Table 14. Subject-Level Localization in Areas Other Than KS Sites - Nuclear Medicine Findings
Navidea Biopharmaceuticals - Study No. NAV3-24
ITD Population (N=xxx)

Group	Number of Subjects	Number Localized (Proportion)	95% Exact One-Sided Binomial CI for Proportion
Cohort 1 IV	xx	xxx (xxx)	(xxx, xxx)
Cohort 2 IV	xx	xxx (xxx)	(xxx, xxx)
Cohort 3 IV	xx	xxx (xxx)	(xxx, xxx)
Cohort 3 SC	xx	xxx (xxx)	(xxx, xxx)
All Cohorts Combined	xx	xxx (xxx)	(xxx, xxx)

Cohort 1 = 100 μ g/5mCi IV; Cohort 2 = 100 μ g/10mCi IV; Cohort 3 = 200 μ g/5mCi IV and SC.
STATKING Clinical Services (DD-MMM-YYYY)
Source Program: xxxxxxx.sas

Page x of y

Table 15. Site-Level Localization in Areas Other Than KS Sites - Nuclear Medicine Findings
 Navidea Biopharmaceuticals - Study No. NAV3-24
 ITD Population (N=xxx)

Group	Anatomical Site	Number (Proportion) of Subjects with Site Localized	95% Exact One- Sided Binomial CI for Proportion
Cohort 1 IV	xxxxxxxxxxxxxxxxxx xxxxxxxxxxxxxxxxxx	xxx (xxx)	(xxx, xxx)
Cohort 2 IV	xxxxxxxxxxxxxxxxxx xxxxxxxxxxxxxxxxxx	xxx (xxx)	(xxx, xxx)
Cohort 3 IV	xxxxxxxxxxxxxxxxxx xxxxxxxxxxxxxxxxxx	xxx (xxx)	(xxx, xxx)
Cohort 3 SC	xxxxxxxxxxxxxxxxxx xxxxxxxxxxxxxxxxxx	xxx (xxx)	(xxx, xxx)
All Cohorts Combined	xxxxxxxxxxxxxxxxxx	xxx (xxx)	(xxx, xxx)

Cohort 1 = 100 μ g/5mCi IV; Cohort 2 = 100 μ g/10mCi IV; Cohort 3 = 200 μ g/5mCi IV and SC.
 STAKING Clinical Services (DD-MMM-YYYY)
 Source Program: xxxxxxx.sas

Table 16. Number and Percent of Subjects with Adverse Events
 Navidea Biopharmaceuticals - Study No. NAV3-24
 Safety Population (N=xxx)

Adverse Event Category ^a :	Cohort 1 (N=xxx)	Cohort 2 (N=xxx)	Cohort 3 (N=xxx)	Overall (N=xxx)
Total Number of Adverse Events	xxx	xxx	xxx	xxx
Subjects with at Least One Adverse Event	xxx (xxx%)	xxx (xxx%)	xxx (xxx%)	xxx (xxx%)
System Organ Class 1	xxx (xxx%)	xxx (xxx%)	xxx (xxx%)	xxx (xxx%)
Preferred Term 1	xxx (xxx%)	xxx (xxx%)	xxx (xxx%)	xxx (xxx%)
Preferred Term 2	xxx (xxx%)	xxx (xxx%)	xxx (xxx%)	xxx (xxx%)
System Organ Class 2	xxx (xxx%)	xxx (xxx%)	xxx (xxx%)	xxx (xxx%)
Preferred Term 1	xxx (xxx%)	xxx (xxx%)	xxx (xxx%)	xxx (xxx%)
Preferred Term 2	xxx (xxx%)	xxx (xxx%)	xxx (xxx%)	xxx (xxx%)

^a Adverse events coded with MedDRA Coding Dictionary Version XXX.
 Cohort 1 = 100µg/5mCi IV; Cohort 2 = 100µg/10mCi IV; Cohort 3 = 200µg/5mCi IV and SC.
 STATKING Clinical Services (DD-MMM-YYYY)
 Source Program: xxxxxxx.sas

Table 17. Summary of Adverse Events
 Navidea Biopharmaceuticals - Study No. NAV3-24
 Safety Population (N=xxxx)

	Cohort 1 (N=xxx)	Cohort 2 (N=xxx)	Cohort 3 (N=xxx)	Overall (N=xxx)
Subjects with at Least One Adverse Event	xxx (xxx%)	xxx (xxx%)	xxx (xxx%)	xxx (xxx%)
Maximum AE Severity Grade				
Mild	xxx (xxx%)	xxx (xxx%)	xxx (xxx%)	xxx (xxx%)
Moderate	xxx (xxx%)	xxx (xxx%)	xxx (xxx%)	xxx (xxx%)
Severe	xxx (xxx%)	xxx (xxx%)	xxx (xxx%)	xxx (xxx%)
Highest Relationship of AE to Tc 99m Tilmanocept				
Definitely Not [n(%)]	xxx (xxx%)	xxx (xxx%)	xxx (xxx%)	xxx (xxx%)
Probably Not [n(%)]	xxx (xxx%)	xxx (xxx%)	xxx (xxx%)	xxx (xxx%)
Possibly [n(%)]	xxx (xxx%)	xxx (xxx%)	xxx (xxx%)	xxx (xxx%)
Probably [n(%)]	xxx (xxx%)	xxx (xxx%)	xxx (xxx%)	xxx (xxx%)
Definitely [n(%)]	xxx (xxx%)	xxx (xxx%)	xxx (xxx%)	xxx (xxx%)
Highest Relationship of AE to Study Procedure				
Definitely Not [n(%)]	xxx (xxx%)	xxx (xxx%)	xxx (xxx%)	xxx (xxx%)
Probably Not [n(%)]	xxx (xxx%)	xxx (xxx%)	xxx (xxx%)	xxx (xxx%)
Possibly [n(%)]	xxx (xxx%)	xxx (xxx%)	xxx (xxx%)	xxx (xxx%)
Probably [n(%)]	xxx (xxx%)	xxx (xxx%)	xxx (xxx%)	xxx (xxx%)
Definitely [n(%)]	xxx (xxx%)	xxx (xxx%)	xxx (xxx%)	xxx (xxx%)
Subjects with at Least One Serious Adverse Event	xxx (xxx%)	xxx (xxx%)	xxx (xxx%)	xxx (xxx%)

Cohort 1 = 100µg/5mCi IV; Cohort 2 = 100µg/10mCi IV; Cohort 3 = 200µg/5mCi IV and SC.

STATKING Clinical Services (DD-MMM-YYYY)

Source Program: xxxxxxxx.sas

Table 18. Number and Percent of Subjects with Treatment Emergent Adverse Events
 Navidea Biopharmaceuticals - Study No. NAV3-24
 Safety Population (N=xxx)

Adverse Event Category ^a :	Cohort 1 (N=xxx)	Cohort 2 (N=xxx)	Cohort 3 (N=xxx)	Overall (N=xxx)
Total Number of Treatment Emergent Adverse Events (TEAEs)	xxx	xxx	xxx	xxx
Subjects with at Least One TEAE	xxx (xxx%)	xxx (xxx%)	xxx (xxx%)	xxx (xxx%)
System Organ Class 1	xxx (xxx%)	xxx (xxx%)	xxx (xxx%)	xxx (xxx%)
Preferred Term 1	xxx (xxx%)	xxx (xxx%)	xxx (xxx%)	xxx (xxx%)
Preferred Term 2	xxx (xxx%)	xxx (xxx%)	xxx (xxx%)	xxx (xxx%)
System Organ Class 2	xxx (xxx%)	xxx (xxx%)	xxx (xxx%)	xxx (xxx%)
Preferred Term 1	xxx (xxx%)	xxx (xxx%)	xxx (xxx%)	xxx (xxx%)
Preferred Term 2	xxx (xxx%)	xxx (xxx%)	xxx (xxx%)	xxx (xxx%)

^a Adverse events coded with MedDRA Coding Dictionary Version XXX.

Cohort 1 = 100µg/5mCi IV; Cohort 2 = 100µg/10mCi IV; Cohort 3 = 200µg/5mCi IV and SC.

STATKING Clinical Services (DD-MMM-YYYY)

Source Program: xxxxxxx.sas

Table 19. Summary of Treatment Emergent Adverse Events
 Navidea Biopharmaceuticals - Study No. NAV3-24
 Safety Population (N=xxxx)

	Cohort 1 (N=xxx)	Cohort 2 (N=xxx)	Cohort 3 (N=xxx)	Overall (N=xxx)
Subjects with at Least One Treatment Emergent Adverse Event (TEAE)	xxx (xxx%)	xxx (xxx%)	xxx (xxx%)	xxx (xxx%)
